HRQOL	Health Related Quality of Life	
IC	Informed Consent	
IL	Inferolateral	
IM	Inferomedial	
IMMPACT	Initiative on Methods, Measurement, and Pain Assessment in Clinical	
	Trials	
IMTA	Institute for medical technology assessment	
IRB	Institutional Review Board	
METC	Medical research ethics committee (MREC); in Dutch: medisch-	
	ethische toetsingscommissie (METC)	
MQS	Medication Quantification Scale	
NRS	Numeric Rating Scale	
NSAID	Non-steroidal anti-inflammatory drugs	
OA	Osteoarthritis	
OKS	Oxford Knee Score	
PCS	Pain Catastrophizing Scale	
PGIC	Patient Global Impression of Change	
QALY	Quality- adjusted Life Year	
RCT	Randomized controlled trial	
RF		
	Radiofrequency	

Cocogen Trial

(S)AE SM	(Serious) Adverse Event Superomedial	
Sponsor	The sponsor is the party that commissions the organisation or performance of the research, for example a pharmaceutical company, academic hospital, scientific organisation or investigator. A party that provides funding for a study but does not commission it is not	
SUSAR	regarded as the sponsor, but referred to as a subsidising party. Suspected Unexpected Serious Adverse Reaction	
ТКА	Total knee arthroplasty	
VAS	Visual analogue scale	
WMO	Medical Research Involving Human Subjects Act; in Dutch: Wet Medisch-wetenschappelijk Onderzoek met Mensen	

Cocogen Trial

SUMMARY

Rationale: Knee osteoarthritis is a progressive degenerative process that affects joint cartilage and the subchondral bone. Approximately 10% to 30% of all osteoarthritis patients suffer from disabling symptoms such as pain, stiffness and loss of function leading to psychological and sleeping disorders and a diminished quality of life. (1-4) When conservative treatment fails to treat the symptoms, a total knee arthroplasty can be performed. (3, 6-9) Due to comorbidities or young age due to the limited lifetime of the prostheses used, the total knee arthroplasty procedure is not suitable for all patients. Also, persistent pain after a total knee arthroplasty is also possible. For these specific groups of patients a radiofrequent treatment of the genicular nerves (superolateral, superomedial and inferomedial) might be an alternative treatment option. Multiple researchers investigated the effect of conventional and later also, cooled radiofrequent treatment of the genicular nerves, with promising results for both techniques. (20-23) However, the techniques have never been compared in a randomised controlled trial.

Objective: The primary goal of this study is to provide an estimate of treatment effects, inclusion rate, and comparability of patients between hospitals to assess the feasibility of conducting a future randomised controlled non-inferiority trial to assess whether the effect of conventional RF treatment of the genicular nerves (superomedial, superolateral and inferomedial) of the index knee on knee pain relief is not inferior to the more expensive cooled RF treatment of the genicular nerves. A secondary goal is to estimate the initial costs and cost-effectiveness of conventional RF treatment compared to cooled radiofrequent treatment so as to determine the need, focus and scope of an economic evaluation alongside the RCT.

Study design This study is a prospective, multicentre, double blind, randomised controlled, non-inferiority pilot study.

Study population: Adult patients (> 18 years) with chronic, moderate to severe knee pain (NRS>4) due to osteoarthritis, radiological diagnosed to be graded 2-4 according to the Kellgren-Lawrence criteria on Rx or MRI or with persistent postoperative moderate to severe knee pain (NRS>4) after total knee arthroplasty.

Intervention (if applicable): One group is treated with a conventional radiofrequent treatment of the genicular nerves (SL, SM, IM) of the index knee. The other group is treated with a cooled radiofrequent treatment.

Main study parameters/endpoints: The primary study outcome parameter is the proportion of patients with a pain intensity reduction of at least 50% at 3 months post intervention compared to baseline. Pain intensity is measured by a Numeric Rating Scale. Secondary parameters include physical functioning, health-related quality of life, emotional outcome, patient satisfaction, side effects, duration effect, medication use, costs and cost

Cocogen Trial

effectiveness. Inclusion rates per patient subgroup (osteoarthritis and post total knee arthroplasty) and per hospital will be monitored as well.

Nature and extent of the burden and risks associated with participation, benefit and group relatedness: After study enrolment and baseline intake, patients are treated and followed at 1, 3, 6 and 12 months after the initial intervention (total of 4 site visits, 1 online visit). Primary endpoint is 3 months post intervention. During the intake a physical examination is done. The treatment itself is performed without sedation and is generally well tolerated without side effects of complications. This study compares two active treatment therapies. Therefore, it is expected that patients from both treatment groups experience similar positive effects regarding pain relief and improved knee function.

Cocogen Trial

1. INTRODUCTION AND RATIONALE

Osteoarthritis is one of the most prevalent chronic diseases and a leading cause of pain and disability. (1) The prevalence of radiographic evidence of knee osteoarthritis in persons older than 55 years varies, depending on which study, between 33 and 68%. Approximately 10% to 30% of those have significant pain and functional impairment. (2) Osteoarthritis is a progressive degenerative process that affects joint cartilage and the subchondral bone. The most important symptoms of knee osteoarthritis are pain, stiffness and loss of function leading to psychological and sleeping disorders and a diminished quality of life. (3, 4)

Treatment options can be divided into non-pharmacological, pharmacological, infiltrations and surgical. Non-pharmacological treatments consists of self-management, lifestyle changes, braces, transcutaneous electrical nerve stimulation, acupuncture and physiotherapy. Pharmacological therapy includes oral analgesics like paracetamol and nonsteroidal anti-inflammatory drugs (NSAID). Patients that are unresponsive to these analgesics are sometimes prescribed strong opioids, although this should be reserved for exceptional cases due to increasing complications related to (ab)use of opioids. (5) Furthermore minimally invasive measurements such as intra articular injections of steroids or viscosupplementation could also provide short term relief. Unfortunately, conservative treatment is often insufficient or associated with side effects. If this is the case, total knee arthroplasty (TKA) can be performed. (3, 6-9)

TKA is not a guarantee of success given that the incidence of postoperative pain and functional limitation can raise as high as 53%. (10-16) Also, there is a group of patients that is not suitable to undergo surgery due to comorbidities or very young age due to the limited lifetime of the prostheses used. In those groups of patients radiofrequent (RF) treatment of the genicular nerves might be an alternative treatment option.

The sensory innervation of the anterior part of the knee is accomplished by articular branches of the femoral, saphenous, obturator, common peroneal, tibial and sciatic nerve. (17-19) Some of these articular branches are called the genicular nerves. Radiofrequent treatment of the genicular nerves is first described by Choi and colleagues in 2011. (17) They targeted the superomedial, superolateral and inferomedial genicular nerves for a conventional RF treatment because these branches are in close proximity with bony landmarks. This makes them a possible target using fluoroscopy. In this double blind randomised trial 38 elderly patient received a conventional RF treatment of 70°C for 90 seconds. They showed significant improvement in visual analogue score (VAS), Oxford knee score (OKS) and global perceived effect (GPE) at 3 months in comparison with placebo.

Cocogen Trial

Since this first report, multiple publications have investigated the effect of conventional and later also, cooled RF treatment of the genicular nerves. (20-23) The use of cooled radiofrequency treatment was first described for the treatment of low back pain after which it found its introduction in the treatment of chronic knee pain in 2015. (22-26) The use of cooled electrodes increases lesion size by removing heat from adjacent tissue and allowing power delivery to be increased without tissue scarring and high impedance. (24) A prior study showed a higher success percentage and possibly a longer effect with the use of cooled radiofrequency. (23) On the other hand, the use of a cooled radiofrequency is associated with a higher product cost. In current practice, cooled RF is increasingly being used and is slowly replacing conventional RF treatment, despite evidence on its superiority. We however, hypothesize that the cheaper conventional RF treatment is not inferior to cooled RF, and may save substantial costs. A comparison between conventional and cooled radiofrequency has not been performed yet.

This protocol outlines a study using a prospective, multicentre, double blind, randomised controlled non-inferiority pilot design to yield important information for the design of a subsequent RCT to test if conventional RF treatment is not inferior to cooled RF, and also to assess the feasibility of conducting such a large RCT in two countries. In addition, we aim to estimate the initial cost-effectiveness of conventional RF treatment compared to cooled RF treatment. The current study is set up to reflect the proposed study design of the future study as close as possible, but results of this pilot study may lead to future design changes.

Cocogen Trial

2. OBJECTIVES

The primary goal is to yield information to inform the design of, and evaluate the feasibility of, a future large randomised controlled non-inferiority trial to assess whether the effect of conventional RF treatment of the genicular nerves (superomedial, superolateral and inferomedial) of the index knee on knee pain relief is not inferior to the more expensive cooled RF treatment of the genicular nerves. The secondary goal is to estimate the initial cost-effectiveness of conventional RF treatment compared to cooled RF treatment so as to determine the need, focus and scope of an economic evaluation in the definitive RCT.

By first performing a pilot study we want to obtain an estimate of treatment effects and an insight into rates of inclusion. We will also be able to judge whether the international collaboration between a Belgian and 2 Dutch hospitals participating in this trial is feasible, and we'll be able to judge whether there are substantial differences in the populations of patients that both countries draw a sample from that may have an effect on the subsequent trial (e.g., the need for multilevel analysis or the need for stratified analysis).

By analysing treatment effect size we will be able to calculate a more accurate sample size for the future RCT. At the moment it is difficult to predict inclusion rates since the patient group of knee pain due to osteoartrose has variety of treatment options of which the investigated treatment is only one.

Cocogen Trial

3. STUDY DESIGN

This study is designed as a prospective, multicentre, double blind, randomised controlled non-inferiority pilot trial. The total follow up time is 12 months with follow up assessments at 1, 3, 6 and 12 months post intervention. It is estimated that the total duration of data collection will cover 2 year. Patients will be randomly selected for treatment with conventional RF treatment or cooled RF treatment of the SL, SM and IL genicular nerves. In total, three hospitals participate in this study: Ziekenhuis Oost-Limburg (Belgium), Maastricht UMC+ (Netherlands) and Rijnstate (Netherlands).

An overview of the main procedures that participants undergo is provided in figure 1, Appendix A.

Cocogen Trial

4. STUDY POPULATION

4.1 Population (base)

Adult patients with chronic, moderate to severe anterior knee pain (NRS>4) due to osteoarthritis, radiological diagnosed to be graded 2-4 according to the Kellgren-Lawrence criteria on Rx or MRI or with persistent postoperative pain after TKA. (27,28) In the patients group with persistent pain after a TKA an extensive orthopaedic workout did not reveal any other therapeutic solutions. Pain is defined as an unpleasant sensory and emotional experience associated with actual or potential tissue damage, or described in term of such damage. (29)

4.2 Inclusion criteria

In order to be eligible to participate in this study, a subject must meet all of the following criteria:

- Age ≥ 18 years
- Able to understand the informed consent form and provide written informed consent and able to complete outcome measures.
- Chronic anterior knee pain (> 12 months) with an NRS > 4 on most or all days for the index knee either constantly or with motion.
- Unresponsive to conventional treatments continued during 12 months including physiotherapy, oral analgesics or intra-articular infiltrations.
- Radiologic confirmation of arthritis of OA grade of 2 (mild), 3 (moderate) or 4 (severe) noted within 6 months for the index knee according the Kellgren Lawrence criteria (27) diagnosed by an independent radiologist with experience in musculoskeletal imaging on Rx or MRI (28) or patients with total knee arthroplasty of the index knee with a negative orthopaedic workout.
- Other therapies (including surgical interventions) for pain in the index knee are allowed for the period of the study follow up as long as they are documented. This is necessary to correctly estimate the costs in the cost effectiveness analyses. Allowing patients to receive additional treatments will also improve the protocol compliance.
- Agree to provide informed consent and to comply with the requirements of this protocol for the full duration of the study

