5.2 Use of co-intervention

It is allowed to use other medication or undergo an intervention as long as documented to be able to adequate estimate costs.

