5.3 Escape medication

The use of all medication is allowed as long as documented. This enables the researchers to adequate estimate costs.

Cocogen Trial

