7.1.1 Main study parameter/endpoint

The primary study parameter is the proportion of patients with a pain reduction of at least 50% at three months post intervention. Pain intensity is expressed as a number from the numerical rating scale. Absolute NRS scores are also collected at each visit. A pain dairy of multiple NRS during 4 days will be collected to achieve a more complete and trustworthy idea of pain.

In this study we will use a threshold of 50% although IMMPACT guidelines only recommend a threshold of 30% because in the clinical setting the 50% threshold is most often used, as well in previous studies. This makes comparison within the literature easier.

NRS is a unidimensional, subjective measurement of pain intensity, expressed by the patient as a number between 0 and 10. It is a 11 point scale in which 0 equals no pain and 10 maximal pain. (35)

Furthermore, at one, three, six and twelve months post intervention the patients are also asked whether the pain is acceptable.

A month is defined as 30 days with 4 days before or after this timepoint.

At 12 months a time window of 2 weeks before and there the timepoint is accepted.

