7.1.2 Secondary study parameters/endpoints

The secondary parameters are:

 Patient self-reported impression of change, measured by the Patient's Global Impression of Change (PGIC) at 1, 3, 6 and 12 months. The impression of change is measured using a 7 point likert scale. (36)

Cocogen Trial

- The change in medication use, measured by the change in Medication Quantification Scale III (MQS III). The MQS is designed as a methodology of quantifying different drug regimens in 1992 and updated in 1998 (MQS II) and 2003 (MQS III) using detriment weights determined by surveying physician members of the American Pain Society. (37) This will be recorded at baseline, 1, 3, 6 and 12 months post intervention.
- The duration of pain relief. This is defined as the time interval in which a NRS reduction of more than 50% is obtained or in which the pain is still acceptable without the usage of other additional therapies (increase in MQS 3 score of more than 50%, intra-articular infiltration, operation)
- The change in physical function from baseline to 3, 6 and 12 months post intervention. This will be measured by the change in the Oxford Knee Score (OKS). (38) The OKS is a patient-reported measure assessing pain intensity and physical function. The list consists of 12 items scored from 1 to 5, with 0 representing normal function/ least symptoms. Objectively, knee function will be measured through goniometry by using the CJOrtho app and by 'timed up and go' test. (39, 40) The measurement of maximal knee flexion and extension is performed in a standardised manner and photos of each position will be kept for review. The 'Timed Up and Go' test assesses patients' functional mobility of the lower extremities. Participants are timed with a stopwatch while standing up from a chair, walking 3 meters (in a comfortable and safe way), come back and sit back in the chair. The objective parameters of physical function will not be obtained at 12 months.

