9. STATISTICAL ANALYSIS

Patient baseline characteristics will be described for both knee pain groups separately, and stratified by treatment allocation using mean and standard deviation or median and interquartile range for continuous variables, and count and percentage for categorical variables. Incomplete patients records will be imputed using multiple imputation to allow analysis on all randomised subjects.

All outcome measures will be computed on the intention to treat sample.

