9.1 Primary study parameter(s)

The primary outcome, the proportion of patients reporting treatment success at 3 months after treatment, will be described per group as count with percentage and 95% confidence interval. In addition, we will report the mean change from baseline on the NRS, including standard deviation and 95% confidence interval. Furthermore, we will compute the difference in proportion of success between groups and the difference in mean change from baseline between groups, both with 95% confidence interval. The lower bound of the 95% confidence interval of the difference will be compared to the non-inferiority limit. However, the latter part will be used only for exploratory purposes, due to the nature of the study design (i.e. pilot study).

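### The 3-month success endpoint credits RF with relief reached after other knee therapy, and no supplementary analysis separates the two

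*Protocol*

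**What the plan says.** Three sections of the protocol permit additional treatment during follow-up.

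- Section 4.2: "Other therapies (including surgical interventions) for pain in the index knee are allowed for the period of the study follow up", provided they are documented. The reasons given are costing and adherence: "Allowing patients to receive additional treatments will also improve the protocol compliance".
- Section 5.2: "It is allowed to use other medication or undergo an intervention as long as documented".
- Section 5.3: "The use of all medication is allowed as long as documented".

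None of them sets a cut-off before the 3-month assessment or discusses the effect on the endpoint.

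Section 7.1.1 defines the primary outcome: "The primary study parameter is the proportion of patients with a pain reduction of at least 50% at three months post intervention". It has no condition on other therapy. Section 9 adds: "All outcome measures will be computed on the intention to treat sample".

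Section 7.1.2 handles the same therapies differently for a secondary outcome. Duration of pain relief is counted "without the usage of other additional therapies (increase in MQS 3 score of more than 50%, intra-articular infiltration, operation").

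Section 9.1 describes the non-inferiority comparison: "The lower bound of the 95% confidence interval of the difference will be compared to the non-inferiority limit". It labels this exploratory. Section 9.2 lets the point estimate on its own be read as pointing to non-inferiority, and in that case uses the pilot's results to size the definitive trial.

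**The concern.** The endpoint measures relief at month 3 by whatever route it came. For a patient whose RF failed and who then improved after an injection, an operation or a large analgesic increase, the relief is credited to the RF technique. The same patient's relief may already have ended under the duration outcome.

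This matters because the hypothesis (section 1) is that conventional RF is not inferior. Section 7.2 says cooled RF may have the higher chance of success. If that is so, the conventional arm has more failures available for conversion, and similar conversion rates in both arms bring the observed success proportions closer together. What is at stake is the effect estimate, the reading in section 9.2, and the rates carried into the planning of the definitive trial.

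**Working it through.** **Inputs from the protocol.** Section 4.4 gives 12 per arm in each of two populations: 12 × 2 × 2 = 48, which reproduces the stated total and means 24 per arm overall. Allocation is 1:1 and patients are unblinded at 6 months (section 7.2). The protocol gives no success rate, no value for the non-inferiority limit and no rate of additional therapy. Every such figure below is an assumption.

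**Formula.** Let p be the success proportion without other therapy, r the share of failures who receive other therapy before month 3, and s the share of those who then reach 50% relief. In each arm

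observed success = p + (1 − p)·r·s.

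With the same r and s in both arms, the difference (conventional minus cooled) is (p_conv − p_cooled)·(1 − r·s).

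**Equal conversion, assumed 40% v 60% (−20 points).**

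| r | s | 1 − r·s | Difference (points) |
|---|---|---|---|
| 0.2 | 0.2 | 0.96 | −19.2 |
| 0.2 | 0.5 | 0.90 | −18.0 |
| 0.4 | 0.6 | 0.76 | −15.2 |

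The shift is 0.8 to 4.8 points. At 24 per arm that is 0.008 × 24 = 0.2 to 0.048 × 24 = 1.2 patients.

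**Precision.** The 95% half-width at 60% v 40% is 1.96 × √(0.24/24 + 0.24/24) = 27.7 points. At 12 per arm it is 1.96 × √(0.24/12 + 0.24/12) = 39.2 points.

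**Other patterns, same 40% v 60%.**

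- Arms truly equal and conversion equal: the difference stays 0.
- Conventional failures treated twice as often (r = 0.4 v 0.2, s = 0.6): 0.40 + 0.60 × 0.24 = 0.544 and 0.60 + 0.40 × 0.12 = 0.648, so −10.4 points.
- Cooled failures treated twice as often: 0.40 + 0.60 × 0.12 = 0.472 and 0.60 + 0.40 × 0.24 = 0.696, so −22.4 points. The direction reverses once conversion in the cooled arm exceeds 0.60/0.40 = 1.5 times that in the conventional arm.

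**Effect on the point-estimate reading.** Take an assumed 50% v 70%, a 15-point limit and 24 per arm. Exact binomial enumeration gives a probability of 0.345 that the point estimate falls on the favourable side of the limit when nobody is converted. With r·s = 0.2 (difference −16) it is 0.455.

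**Effect on planning.** With an assumed 15-point limit, 80% power and one-sided 0.025, n per arm = (1.96 + 0.842)² × (sum of p(1 − p)) / (0.15 − deficit)², where (1.96 + 0.842)² is about 7.85.

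- 60% v 70%, no conversion: 7.85 × 0.45 / 0.05² gives 1413.
- r·s = 0.2, so 68% v 76%: 7.85 × 0.40 / 0.07² gives 641.
- Equal arms at 60%: 168. With r·s = 0.2, so 68% in both: 152.

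The planning figure is sensitive when a true deficit lies near the limit, and hardly moves when the arms are equal.

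**The case against.** The strongest reply is that counting the month-3 outcome whatever else was given is a recognised treatment-policy approach. The protocol chose it openly, and it suits the cost-effectiveness aim. Duration of relief is also a different construct, since it counts acceptable pain as well. All of this stands: the endpoint is not an error, and section 7.1.2 does not strictly contradict section 7.1.1.

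Section 1 says the pilot mirrors the planned trial as closely as possible. If that trial keeps the same co-treatment policy and endpoint, the observed rates are the right planning input. This stands too. The rates mislead only if the definitive trial is meant to measure the effect of RF itself.

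Conversion may also be uncommon. Section 4.2 requires failure of 12 months of conventional treatment, and section 4.1 says orthopaedic work-up found no other solution in the arthroplasty patients. Large values of s are therefore doubtful.

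Much unequal use would be visible anyway. MQS III and cost data are collected by month 3 (Appendix E), and MQS change and duration of relief are compared between arms. Still, no month-3 success proportion that sets aside additional therapy is named. An analysis plan not shown here might add one, but the endpoint rule itself is fixed in the protocol.

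A reader might infer that analysing only the intention-to-treat sample is the cause and that a per-protocol analysis would cure it. The document does not support that. Co-treatment is permitted, so these patients are not deviators, and an ordinary per-protocol set would keep them.

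**Conclusion.** The point holds as a cheap improvement. Relief reached after other index-knee therapy is scored as success of the allocated technique, and nothing stated shows how far the primary result depends on this.

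A reader might infer that the rule always favours non-inferiority. It does so only if the arms truly differ and failures are converted at similar rates, or more often in the worse arm. Blinding to 6 months makes treatment driven by response rather than by known allocation the more plausible pattern, but does not guarantee it. Nor does additional therapy alone make a patient a success: the 50% threshold must still be met.

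For an assumed −20 points, equal conversion gives about −19 to −15. That is small beside a half-width of about 28 points in a comparison labelled exploratory. The consequence lies in the point-estimate reading of section 9.2 and, if the definitive trial targets the effect of RF itself, in its planning rates. All sizes rest on assumed r, s, success rates and limit.

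**What to change.** Keep the intention-to-treat treatment-policy analysis and leave every treatment permission as it is. In section 9.1, pre-specify a supplementary analysis of the 3-month success proportion in which a patient is a non-success if either applies:

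- an intra-articular infiltration or an operation on the index knee before the 3-month assessment; or
- an MQS III score at the 3-month visit more than 50% above baseline, with a stated rule for a baseline score of zero, where a percentage increase is undefined.

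The score at the 3-month visit is used, rather than any earlier rise, because section 5.1 warns of a transient pain increase after the procedure. A brief early rise in analgesics should not turn a later responder into a non-success.

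Report additional therapy by arm, interpret non-inferiority with both results in view, and derive the planning rates for the definitive trial the same way. A per-protocol analysis is not needed for this problem.

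The cost is a few lines of text and one extra table. The therapies must already be documented (section 4.2) and MQS III is already recorded at baseline and 3 months (Appendix E). Success percentages in the supplementary analysis will be somewhat lower.
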